**4. Treatment Phase.** Subjects who qualify for randomization will enter the Treatment Phase. They will be randomly assigned to parallel study arms in a 2:1 ratio of rizatriptan 10 mg encapsulated tablets or look-alike placebo capsules. Subjects will treat three vestibular attacks that manifest with Grade 3/2 vestibular symptoms. Associated symptoms, including headache, need not be present and may be of lesser severity. Headaches without vestibular symptoms are not eligible for study treatment, but may be treated in the subjects' usual manner. Subjects will be instructed to ingest one study capsule as soon as possible after onset of Grade 3/2 vestibular symptoms. They will record treatment response in their Vestibular Symptom Diaries by rating the severity of vestibular and associated symptoms at the time they take study medication and at 0.5, 1, 2, 4, 24, and 48 hours post-dose. Subjects will record adverse effects in accordance with the Common Toxicity Criteria Scale 4.0, treatment satisfaction on the TSQM, and quality of life on the SF-12 at 48 hours post-dose. Then they will contact study personnel by phone to review the attack and treatment response.

Subjects will treat one attack with study medication in a 48-hour period. Repeat dosing of study medication within 48 hours will not be permitted. Subjects must have a vertigo-free period of at least 48 hours before treating a subsequent vestibular attack with study medication. The relatively short plasma half-life of rizatriptan (2-2.5 hours) justifies the 48-hour wash out period. Subjects may use other medications to treat residual symptoms (see Concomitant Medications) but must wait at least 1 hour after taking the study medication. Additional treatments will be reported to study personnel together with other attack data. Subjects will remain in the Treatment Phase until they have treated three separate vestibular attacks, experience serious or intolerable adverse effects, withdraw for other reasons, or reach the end of the study. Study personnel will conduct telephone assessments on a monthly basis as they did during the Observation Phase. Extra visits to study clinics will be arranged as needed to re-evaluate subjects' health and treat problematic symptoms.

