## **J. Statistical Methods**

**1. Power Analysis.** The primary goal of this Phase II study is to demonstrate sufficient superiority of rizatriptan over placebo in the main outcome measure, 1a(1), to warrant a future Phase III trial. In the previous triptan study for VM (see Prior Controlled Study of Triptans for VM), the response rate for active drug was 3/8 (38%) versus 2/9 (22%) for placebo. If the small sample from that failed trial reflected a true response, then the odds ratio favoring the triptan for VM would be 2.1. To improve our estimate, we examined the results of two large registration trials that used a simple randomization design similar to the present proposal to test rizatriptan for conventional migraine. Those studies had response rates of 74% and 77% for rizatriptan versus 28% and 37% for placebo giving odds ratios of 7.4 and 5.7 favoring rizatriptan. The lower response rates in the VM trial most likely reflected the inadequate sample size, but could suggest that triptans are less effective for VM than conventional migraine. To account for this possibility, we took the limited results of Neuhauser, et al. as a worst-case scenario for our sample size calculation. Focusing on the main outcome measure, 1a(1), in this double-blind, randomized trial, with PASS simple randomization design and using a type I error of 0.05, type II error of 0.2 (equivalent to power of 80%), two-sided tests, then treating 120 subjects (with 2:1 ratio for treatment and placebo) will allow us to detect an odds ratio as small as 3.2. Thus, the plan to enroll 200 subjects in the Observation Phase and select 120 for the Treatment Phase will be sufficient, even if the response of VM to rizatriptan proves to be only half that of conventional migraine. Phase II trials typically gather data on secondary outcomes (e.g., 1a(2)-1d(2)) and other variables (2a-c) to inform the design of Phase III trials, but sample sizes need not be planned to demonstrate significant differences in these variables.

**2. Randomization.** A randomization scheme will be developed to assign the 120 patients expected to be included in the Treatment Phase to parallel treatment arms in a 2:1 ratio of active drug:placebo.

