7. Interim analysis: We will conduct an interim analysis at study midpoint without breaking the blind to assess (1) recruitment, (2) safety, and (3) efficacy. Plans for shortfalls in recruitment are noted below. We will terminate the study for insufficient safety if there is a statistically significant difference between arms in adverse events of greater than minor severity, or for lack of efficacy if response rates are <25% in both arms, i.e., no better than placebo rates in previous triptan trials. We will continue the study if the primary outcome, 1(a)1, is >25% in at least one arm, but not statistically different between arms. If the primary outcome is statistically different, then we will terminate the study because the primary aim will be met. We will break the blind and identify the results as positive (rizatriptan superior to placebo) or negative (rizatriptan inferior to placebo).

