## V. STUDY OVERSIGHT

The PI and Co-PI will have primary responsibility for the conduct of this clinical trial. A Data Safety Monitoring Board (DSMB) with oversight responsibility will be appointed by NIDCD. The DSMB will review subject accrual, frequencies and patterns of all adverse events, and protocol compliance on a quarterly basis and will make recommendations to the NIH regarding the continuation status of the protocol. Co-Investigator [name] will compile clinical data to prepare the reports for DSMB reviews.

The Principal Investigator, Co-PI and their research teams (co-investigators, research nurses, research coordinators, and others) will be responsible for identifying adverse events. Aggregate reports detailed by severity, attribution (expected or unexpected), and relationship to the study drug/study procedures will be made available by the DSCC for site review. A separate report detailing protocol compliance will also be available from the DSCC for site review monthly. The research team will review these reports monthly and determine whether the protocol or informed consent document requires revision based on the reports.

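### The midpoint interim is described as blinded, but its rules need results by arm, 2:1 allocation shows the active arm to anyone who sees arm sizes, and no firewall is specified

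*Combined protocol and SAP*

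**What the plan says.** Section III.J.3, item 7 introduces the interim with the sentence "We will conduct an interim analysis at study midpoint without breaking the blind to assess (1) recruitment, (2) safety, and (3) efficacy". It then gives four rules:

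- Stop for safety on a "statistically significant difference between arms in adverse events of greater than minor severity".
- Stop for lack of efficacy if response is below 25% in both arms.
- "We will continue the study if the primary outcome, 1(a)1, is >25% in at least one arm, but not statistically different between arms".
- Stop if the primary outcome differs significantly. Only here does the text have the blind broken, so that the result can be labelled as favouring rizatriptan or placebo.

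Section III.J.2 assigns subjects to "parallel treatment arms in a 2:1 ratio of active drug:placebo", and III.D.4 repeats the ratio. No block size or stratification is given. Section III.K places the interim at month 33.

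On who handles the data, III.I puts all statistical analysis at the Data & Statistical Coordinating Center (DSCC). Section V has the DSMB review accrual, adverse events and compliance each quarter, and adds: "Co-Investigator [name] will compile clinical data to prepare the reports for DSMB reviews". Item 7 writes every decision in the first person plural. It does not say who sees the comparison by arm.

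**The concern.** An interim can be called blinded if the data are pooled, or if the by-arm results go only to people outside trial conduct. Item 7 provides for neither. The comparison is by arm, and its recipients are unnamed. The only protection left is that the arms carry codes until a significant difference appears, and a 2:1 ratio defeats codes as soon as denominators are visible.

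The stake lies in the branch where the trial continues. Study personnel still enrol and instruct subjects and discuss each treated attack (III.D.4: "Then they will contact study personnel by phone to review the attack and treatment response"), and investigators may withdraw subjects (V.F). The primary outcome, 1a(1), is a subject's own severity grade at one hour, and 1d(2) counts discontinuations for adverse events. Under III.J.3, item 4, both bear on the principal result. Endpoints of this kind rely heavily on nobody in trial conduct knowing how the arms are doing.

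**Working it through.** **The plan's own figure.** The plan gives no figure for masking. The one calculation in the same section is the detectable odds ratio of 3.2 with 120 subjects at 2:1. With 22% response on placebo, the rizatriptan odds are 3.2 × 0.22/0.78 = 0.903, a rate of 47.4%. With 80 versus 40 subjects and a two-sided test at 0.05, power is 79.0%, and the smallest odds ratio detectable at 80% power is 3.24. The figure reproduces, and this point does not affect it.

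**Inputs.** The probability of allocation to rizatriptan is 2/3 (III.D.4, III.J.2). Planned randomisation is 120 (III.J.2). The interim is at month 33, and subjects still active at month 57 get a final visit (III.K). The number randomised by month 33 is not stated. I take 20 to 60, where 60 = 120/2 reads the midpoint as half the sample.

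**Step 1: do the rules need arm-level data?** The safety and efficacy rules are tests between arms. The futility rule needs the rate in each arm. The continue rule needs both the rates and a test. None can be applied to pooled data.

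**Step 2: how well do coded labels hide the active arm?** Under simple randomisation the rizatriptan count X among n subjects is Binomial(n, 2/3). The chance that rizatriptan is the larger arm is P(X > n/2):

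| n randomised | rizatriptan larger | tie | placebo larger |
|---|---|---|---|
| 20 | 0.908 | 0.054 | 0.038 |
| 30 | 0.957 | 0.025 | 0.019 |
| 40 | 0.979 | 0.012 | 0.010 |
| 60 | 0.994 | 0.003 | 0.003 |

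**Step 3: what does a given split tell the reader?** For arms of size a > b with d = a − b, the likelihood ratio that the larger arm is rizatriptan is [(2/3)^a (1/3)^b] / [(1/3)^a (2/3)^b] = 2^d. With labels assigned at random, the probability is 2^d/(2^d + 1):

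- 40 versus 20, the expected split at 60: d = 20, above 0.99999.
- 35 versus 25: d = 10, 1024/1025 = 0.999.
- 31 versus 29, an unusually even split: d = 2, 4/5 = 0.80.

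Under 2:1 blocking, each completed block holds twice as many rizatriptan as placebo subjects, so identification is effectively certain.

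**Step 4: attack counts.** The primary outcome is a proportion of attacks, so an efficacy table may show attacks and not subjects. The results abstract in the combined document reports 153 versus 92 analysed attacks, a ratio of 153/92 = 1.66. That is a final figure, not an interim one, but it shows that attack denominators can also point to the larger arm.

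**Step 5: what arm sizes do not reveal.** They identify the coded arm as a whole. Placing a given subject in an arm also needs a file linking subject identifiers to the code. Randomisation codes sit in the Research Pharmacy record (III.F), and DSCC analysis files carry only encrypted identifiers (III.I).

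**Step 6: time at risk.** If the trial continues, conduct runs from month 33 to as late as month 57, up to 57 − 33 = 24 months.

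**The case against.** A reader might infer that the investigators are unblinded at the interim. The documents do not say that. All analyses are at the DSCC, and the first person plural in section III.J also covers ordinary analysis work. The DSCC could return only a decision, or percentages without denominators. The sentence about the co-investigator mentions clinical data and does not say by arm. This stands: the supported statement is that investigators can learn the results, because nothing prevents it.

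A reader might also infer that staff would know each subject's treatment. Arm sizes do not show that, and without it the listed contacts cannot readily favour one arm over the other. The telephone review comes after the 48-hour ratings, so it follows the one-hour grade for that attack. This also stands and narrows the harm. What remains is knowledge of the aggregate direction, size and tolerability, which can still colour recruitment, the instruction of later subjects, the handling of adverse events and withdrawal decisions.

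Third, exposure arises only when the arms do not differ significantly. That is true, but a non-significant midpoint result still shows a direction and a size.

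Fourth, the DSMB advises on continuation, and safety data are examined with it every three months (III.K, V). That covers part of the safety side. It does not assign interim efficacy to anyone, and no closed session is described.

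Finally, it is tempting to say that half the subjects would be treated after the look. With no randomised count for month 33, that is only an assumption.

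**Conclusion.** The concern holds in a limited form. Item 7 claims that the blind is kept, but with 2:1 allocation coded labels alone do not keep it from anyone who sees arm sizes. Such a person would identify the rizatriptan arm with probability about 0.91 to 0.99 for 20 to 60 randomised under simple randomisation, and almost surely under blocking. Both the count at month 33 and the randomisation method are assumptions, since the plan states neither, but the conclusion is the same across the range.

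The plan names no recipient and no firewall, and the DSMB's listed remit omits interim efficacy. The trial team can therefore carry on with knowledge of the interim efficacy and tolerability results by arm. The documents do not show that this happened, that individual allocations would be known, or how large any resulting bias would be. This should be fixed. It does not by itself invalidate the trial.

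**What to change.** In III.J.3, item 7, replace the claim that the blind is not broken with three statements:

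- A DSCC statistician with no subject contact prepares the by-arm safety and efficacy comparison.
- The comparison goes only to the DSMB, in closed session.
- Investigators, coordinators and anyone compiling open reports receive only the recommendation to continue or stop.

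In Section V, add interim efficacy review to the DSMB's remit.

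The combined document already carries a results abstract, which does not mention the interim. If the interim was run, the trial report should state who saw results by arm.

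The cost is a few sentences. The DSCC and a quarterly DSMB already exist, and the sample size does not change. The downside is that investigators give up direct sight of the interim results.

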## III. APPROACH

We propose a two-center, randomized, double blind, placebo-controlled, parallel, three-episode, clinical trial of rizatriptan 10 mg oral tablets versus placebo for treating spontaneous vestibular attacks in patients with VM.

Our primary Specific Aim is to test hypotheses 1a-1d that rizatriptan will be:

- 1a. Superior to placebo in reducing the severity and duration of vestibular attacks as measured by:
  - (1) Proportion of treated attacks in which subjects experience a reduction in severity rating from Grade 3/2 to Grade 1/0 at one hour after taking study medication (see below for rating description). This is the main outcome measure; 1a(2)-1d(2) are secondary outcome measures.
  - (2) Proportion of treated attacks in which subjects achieve sustained relief (i.e., vestibular symptom severity rating of Grade 1/0) for 24 hours after taking study medication, without use of non-study therapies.
  - (3) Proportion of treated attacks in which subjects experience freedom from vestibular symptoms (i.e., severity rating of Grade 0) at one hour after taking study medication.
  - (4) Use of fewer non-study therapies after each attack treated with study medication.
- 1b. Superior to placebo in reducing severity of symptoms associated with vestibular attacks as measured by:
  - (1) Proportion of treated attacks in which subjects experience relief (reduction to Grade 1/0) from VM-associated symptoms (e.g., nausea, vomiting, motion sensitivity, gait disturbance, headache, photophobia, and phonophobia) at one hour after taking study medication.
  - (2) Proportion of treated attacks in which subjects achieve sustained relief from VM-associated symptoms for 24 hours after taking study medication without use of non-study therapies.
- 1c. Superior to placebo on treatment satisfaction and health-related quality of life as measured by:
  - (1) Scores on the Treatment Satisfaction Questionnaire for Medication (TSQM) at 48 hours after each attack treated with study medication
  - (2) Scores on the Short Form 12 (SF-12) at 48 hours after each attack treated with study medication
- 1d. Tolerated as well as placebo by patients with VM as measured by:
  - (1) No greater rate of treatment-emergent serious adverse events reported on the NCI Common Toxicity Criteria Scale 4.0^59 obtained 48 hours after each attack treated with study medication.

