4. We will use this 3-step analysis procedure to test all outcome measures for hypotheses 1a-1d. However, the principal result of the study will be determined by the findings of bivariate analyses and multivariate modeling of the main outcome measure, 1.a.(1), plus favorable findings on tolerability measures, 1d(1)-1d(2). We will include all subjects who treat at least one vertigo attack with study drug (i.e., intent-to-treat analysis). A statistically significant result favoring rizatriptan over placebo on 1a(1) and absence of statistically significant differences on 1d(1)-1d(2) will support development of a Phase III clinical trial of rizatriptan for treating vestibular attacks in patients with VM. The design of future trials will also be informed by results of tests of secondary measures 1a(2)-1c(2). We did not hypothesize equal tolerability for rizatriptan and placebo, but rather an absence of significantly higher rates of serious adverse effects and drug-related treatment discontinuation, so our statistical analyses of measures 1d(1)-1d(2) will not include equivalence tests.

[figure not shown]

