### **D. Potential Risks**

**1. Adverse Effects of Medication:** The primary risk to subjects will be the potential for adverse effects of study medication. There is a wealth of data documenting the safety and efficacy of rizatriptan in treating patients with migraine. In this randomized trial, we will use a dose of rizatriptan that is generally well tolerated by patients with migraine (10 mg). Common adverse events include: drowsiness (4-10%), dizziness (4-10%), nausea (4-8%), fatigue (1-7%), tingling or numb feeling (4%), dry mouth (3%), muscle pain or cramps (2%), and tightness in the neck or jaw (2%), tremors, chills, and flushing (feeling of warmth). Serious adverse events include chest pain (3%), hypertension, coronary artery spasm, myocardial infarction, peripheral ischemia, ventricular arrhythmia, ischemic colitis, anaphylaxis, angioedema, analgesic overuse headache, cerebrovascular accident, and serotonin syndrome.

**2. Loss of Confidentiality:** There is also a risk of loss of confidentiality if identifying information and data from medical records or study forms are inadvertently released.

**3. Time Demands:** This study places demands on subjects' time for completion of the Vertigo Symptom Diary and self-report instruments as well as monthly telephone appointments with investigators or research coordinators. The Vertigo Symptom Diary will have to be completed during and after each attack. Subjects will

track vertigo, headache, and associated symptoms in their diaries. They will rate each symptom using a single number from 0-3 at 0.5, 1, 2, 4, 12, 24, and 48 hours after the onset of each vertigo attack, which is expected to take 10-20 seconds at each time point or less than 3 minutes total per attack. Over the course of the study, subjects also will be required to complete 20 rating scales ranging in length from 7 to 36 questions. Each of these will take 1-5 minutes to complete for a total of about 80 minutes over the entire study. Telephone appointments are expected to be less than 30 minutes long on a monthly basis. During study Visit 1 only, subjects will complete a personality questionnaire that will take 30-40 minutes.

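### The interim safety stop names no direction and is applied without unblinding, so an adverse-event excess on placebo would also end the trial for insufficient safety

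*Combined protocol and SAP*

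**What the plan says.** Section III.J.3, step 7, sets up the interim look: "We will conduct an interim analysis at study midpoint without breaking the blind to assess (1) recruitment, (2) safety, and (3) efficacy". Under the safety heading, the investigators will "terminate the study for insufficient safety if there is a statistically significant difference between arms in adverse events of greater than minor severity". The sentence names no arm, sign, test, significance level or list of events. For efficacy the same step says: "If the primary outcome is statistically different, then we will terminate the study because the primary aim will be met". Only after that efficacy stop does the plan break the blind and read which arm did better. No such step follows the safety stop, and no order of precedence between the two stops is given.

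Elsewhere the safety question has a direction. Hypothesis 1d(1) in section III is "No greater rate of treatment-emergent serious adverse events reported on the NCI Common Toxicity Criteria Scale 4.0", and 1d(2) is likewise no greater rate of discontinuation for adverse events. Step 4 of III.J.3 ends by explaining that the hypothesis is an "absence of significantly higher rates of serious adverse effects and drug-related treatment discontinuation". The go criterion earlier in step 4 is not directional, however: it asks for no statistically significant differences on 1d(1)-1d(2).

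**The concern.** A safety stop is meant to protect subjects from the test drug. Here the condition is met equally by an excess on rizatriptan and by an excess on placebo, and the action is mandatory in both cases. With the blind kept, nothing in the rule separates the two. The trial could be closed and labelled unsafe when the drug arm had fewer events, and the primary question would then be left with about half the planned data. The same wording in the go criterion means that a significantly lower serious-event or discontinuation rate on rizatriptan would, read literally, fail to support a Phase III trial.

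**Working it through.** **The plan's own figures.** The documents give no operating characteristics for the safety rule, so there is none to reproduce. The stated design does reproduce. With placebo response 22% and odds ratio 3.2, the rizatriptan odds are 3.2 × 0.22/0.78 = 0.903, a rate of 47.4%. With 80 v 40 subjects and two-sided 0.05, power is 79.0% against the stated 80%.

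**Inputs for the safety rule.** The 2:1 allocation and 120 subjects come from III.J.1. The following are assumptions:
- 40 rizatriptan and 20 placebo subjects at the interim. Section III.K gives month 33 but no count, so 20 v 10 and 80 v 40 are also shown.
- One comparison of the proportion of subjects with an event, two-sided at 0.05. This level is stated for the primary outcome only.
- All event rates for adverse events above minor severity.

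**Test.** With x_P events in 20 placebo and x_R in 40 rizatriptan subjects, and p = (x_P + x_R)/60,

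z = (x_P/20 − x_R/40) / √[p(1 − p)(1/20 + 1/40)]; stop if |z| > 1.96.

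Two placebo events against none on rizatriptan give p = 0.0333 and z = 0.10/√(0.0333 × 0.9667 × 0.075) = 0.10/0.0492 = 2.03: stop. In the other direction, six rizatriptan events against none give 0.15/0.0822 = 1.83, no stop; seven give 0.175/0.0879 = 1.99, stop. Because placebo is the smaller arm, this test reacts to fewer events there when events are rare.

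**Chance of stopping**, from exact binomial enumeration over all (x_P, x_R), 40 v 20 subjects, equal rates:

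| Rate in both arms | Placebo excess | Rizatriptan excess | Placebo share of false stops |
|---|---|---|---|
| 5% | 3.9% | 0.1% | 97% |
| 10% | 2.7% | 1.3% | 68% |
| 20% | 2.6% | 2.1% | 56% |

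With Fisher's exact test the placebo-excess figures are 1.5%, 2.3% and 1.8%. With 20 v 10 subjects (z test) they are 3.1%, 3.6% and 2.7%; with 80 v 40, 3.0%, 2.7% and 2.7%.

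**If rizatriptan causes more events** (40 v 20 subjects; rates are rizatriptan v placebo):

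| Rates | Placebo excess | Rizatriptan excess |
|---|---|---|
| 8% v 4% | 0.8% | 1.7% |
| 10% v 5% | 0.5% | 3.6% |
| 15% v 5% | 0.1% | 15% |

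**If symptoms of the treated attack were counted** and placebo had twice the rate, the placebo-excess stop would be 18% at 10% v 20% and 38% at 20% v 40%. At 20 v 10 subjects these become 12% and 22%; at 80 v 40, 33% and 65%.

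**After the fix.** If only a rizatriptan excess counts, at the same critical value, the placebo-excess column becomes zero by construction and the rizatriptan-excess column is unchanged.

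**The case against.** A reader might infer that the trial would be closed because the drug works: dizziness and nausea are listed as expected adverse events (IV.D.1 and V.B), they are also symptoms of the attack, and an effective drug leaves fewer of them. The documents do not support this as a finding. It needs persisting attack symptoms to be logged as adverse events above minor severity, and several places point the other way. Dosing requires Grade 3/2 vestibular symptoms already present. Attack symptoms are rated in the diary, and toxicity is recorded separately (III.D.4, III.E). Adverse effects are called treatment-emergent in the Specific Aims and in 1d(1). Section V.A ties an adverse event to participation in the study. None of these expressly excludes attack symptoms, and treatment-emergent is neither defined nor used in the stopping rule, so the route stays open but conditional.

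The reported results also give it no support. At 24 hours, unsteadiness/dizziness was not relieved in 29/149 (19%) rizatriptan v 36/88 (41%) placebo attacks, yet the only side-effect difference reported is more mild/moderate fatigue and drowsiness on rizatriptan. These are final, attack-level data, so this is indicative only.

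A second tempting reading is that the final criterion is directional and confined to serious events, so the interim rule contradicts it on both counts. It does not hold in that form. The go criterion is itself undirected, and 1d(2) counts discontinuation for events of any type or severity. Watching a broader class of events at the interim than at the end is a design choice, not in itself an error.

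There are also safeguards. If the drug works on the primary outcome, the efficacy stop may fire, and it unblinds. The DSMB reviews adverse events every quarter (III.K, V). With 2:1 allocation, coded arms can be told apart by size. These make a wrong-direction closure less likely. They do not repair the rule, because step 7 makes termination mandatory, gives the DSMB no part in it, sets no precedence between stops and makes no use of direction even if the arms can be identified.

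**Conclusion.** The point holds as an inconsistency in the stated rule. The interim safety stop is undirected and masked, a significant placebo excess meets it literally, and this contradicts the directional hypotheses in 1d and at the end of step 4. The go criterion in step 4 shares the fault.

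The size is modest. Under the stated assumptions the chance of a placebo-excess stop is about 3-4% at equal event rates of 5-20%, more than half of all false safety stops, and it is under 1% in the scenarios where rizatriptan causes more events. The 18% and 38% figures apply only if attack symptoms are counted as adverse events, at rates that the documents do not give, and should not be quoted as the expected effect of the rule.

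**What to change.** Reconcile the safety sentence of step 7 and the go criterion of step 4 with the direction already used in 1d(1) and 1d(2), an excess on rizatriptan. State the test and significance level for the interim comparison. Have direction read with arm identity by the DSMB or an unblinded statistician before the safety stop is applied. Say that the rule uses treatment-emergent events, as in the Specific Aims and 1d(1), and define that term so that the handling of treated-attack symptoms is explicit. Whether the interim and final event classes should match is for the sponsor and DSMB to settle.

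The cost is wording in the protocol and the DSMB's instructions; sample size and data collection do not change. The downside is that someone outside the study team must see arm identity at the interim.

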## **K. Timeline of Study**

During the first three months of the study, we expect to finalize data entry methods and train study personnel. Then we will begin recruitment into the Observation Phase. Patients will remain in the Observational Phase until they have two qualifying attacks or for a maximum of 12 months. These phases will continue for a total of four years. Subjects who are active in the Treatment Phase at month 57 will be scheduled for a Final Visit (Visit 3) regardless of how many attacks they have treated. We will conduct reviews every 3 months to evaluate enrollment and the flow of subjects through all parts of the study to determine whether recruitment efforts have to be extended and to examine safety data with the DSMB. Analysis of data from the Observation Phase will begin as soon as that portion of the study is closed. Interim analysis will occur at month 33. Analysis of treatment outcome data will commence after the last subject has a Final Visit.

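### The interim lack-of-efficacy rule uses absolute response below 25% in both arms, so its behaviour follows the placebo rate rather than the treatment effect, and it overlaps the success rule without precedence

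*Combined protocol and SAP*

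**What the plan says.** Section III.J, item 7 of the combined protocol and SAP has three rules that use the primary outcome, 1a(1).

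- **Stop for lack of efficacy:** "for lack of efficacy if response rates are <25% in both arms, i.e., no better than placebo rates in previous triptan trials".
- **Continue:** "We will continue the study if the primary outcome, 1(a)1, is >25% in at least one arm, but not statistically different between arms".
- **Stop for success:** "If the primary outcome is statistically different, then we will terminate the study because the primary aim will be met". The blind is then broken and the result is labelled positive or negative.

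On timing the plan says "We will conduct an interim analysis at study midpoint without breaking the blind", and section III.K adds "Interim analysis will occur at month 33". No number of subjects or attacks, no interim significance level and no operating characteristics are given.

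The earlier response rates are in the power analysis (section III.J, item 1). The zolmitriptan trial in vestibular migraine, taken as the worst case for sample size, had "3/8 (38%) versus 2/9 (22%) for placebo". The two rizatriptan registration trials had "response rates of 74% and 77% for rizatriptan versus 28% and 37% for placebo".

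**The concern.** The trial asks whether rizatriptan beats placebo, and section III.J.3, item 4 defines success by a significant difference between arms. The futility rule looks only at whether both observed rates are low. Two equal arms at 37% give no sign of benefit but do not trigger it; two clearly different arms below 25% do.

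The rationale for 25% is also loose. The cited placebo rates are 22%, 28% and 37%, so the threshold sits above one and below the other two. If placebo response resembles that in the registration trials, the futility look has little purpose.

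The lack-of-efficacy and success rules can be satisfied by the same data. Both end the study, so what is at stake is the label: ineffective or successful. Finally, if the higher observed rate is exactly 25% and the arms do not differ significantly, neither the stop rule nor the continue rule applies.

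**Working it through.** **1. The plan's own figure.** Inputs: 120 subjects at 2:1 (80:40), "using a type I error of 0.05, type II error of 0.2 (equivalent to power of 80%), two-sided tests", detectable odds ratio 3.2. I take the 22% placebo rate as the base.

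- Active rate: 0.22/0.78 × 3.2 = 0.903 odds; 0.903/1.903 = 0.474.
- Pooled rate: (80 × 0.474 + 40 × 0.22)/120 = 0.390. Standard error under the null 0.0944, under the alternative 0.0861.
- Power = Φ[(0.254 − 1.96 × 0.0944)/0.0861] = Φ(0.805) = 0.79.

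The stated 80% is reproduced. The documents give no corresponding figure for the interim rule.

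**2. Assumptions for the interim.** Half of 120 subjects, so 40:20. Each contributes one, two or three attacks, giving 40:20, 80:40 or 120:60 attacks, treated as independent. Within-subject correlation would move the larger columns towards the 40:20 column. Interim significance: uncorrected chi-square at two-sided 0.05.

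**3. Probability of stopping for lack of efficacy.** With independent arms,

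P(stop) = P(X_T < 0.25 n_T) × P(X_C < 0.25 n_C), X binomial.

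Worked case, 22% in both arms, 40:20: P(X_T ≤ 9) × P(X_C ≤ 4) = 0.618 × 0.542 = 0.335.

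| True rates, active v placebo | 40:20 | 80:40 | 120:60 |
|---|---|---|---|
| 22% v 22% | 0.33 | 0.43 | 0.50 |
| 28% v 28% | 0.085 | 0.067 | 0.053 |
| 30% v 30% | 0.047 | 0.026 | 0.016 |
| 37% v 37% | 0.003 | 0.0003 | <0.0001 |
| 38% v 22% | 0.016 | 0.003 | 0.0006 |
| 47.4% v 22% (OR 3.2) | 0.0006 | <0.0001 | <0.0001 |
| 26.2% v 10% (OR 3.2, hypothetical) | 0.35 | 0.36 | 0.35 |
| 21.8% v 8% (OR 3.2, hypothetical) | 0.62 | 0.72 | 0.78 |

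The last two rows lie below every placebo rate the plan cites. The three equal-rate rows at 22%, 28% and 37% have the same treatment effect, none, yet the stopping probability runs from one half to almost zero. The three OR 3.2 rows share one odds ratio and run from almost zero to 0.78.

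**4. Overlap with the success rule.** Take 29/120 (24.2%) versus 5/60 (8.3%). Pooled rate 34/180 = 0.189; standard error √(0.189 × 0.811 × (1/120 + 1/60)) = 0.0619; z = 0.158/0.0619 = 2.56; p = 0.011 (Fisher 0.014). Both rules are met. Smaller examples: 9/40 versus 0/20 (p=0.021) and 19/80 versus 3/40 (p=0.030). The probability of joint firing is 0.02% or less at 38% or 47.4% versus 22%. It is 4-19% in the hypothetical 10% placebo case and 8-47% in the 8% case.

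**5. Exactly 25%.** Results such as 10/40 with 5/20 are neither below nor above 25% and not significantly different, so no rule covers them.

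**6. A comparative alternative.** Normal approximation, half information, final critical value 1.96, design drift θ = 1.960 + 0.842 = 2.80. Conditional power given interim z₁ is

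CP = Φ[(√0.5 z₁ + 0.5θ − 1.96)/√0.5].

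Setting CP = 0.20 gives z₁ = −0.051.

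- Useless drug: P(stop) = Φ(−0.051) = 0.48.
- Design effect: P(stop) = Φ(−0.051 − √0.5 × 2.80) = Φ(−2.03) = 0.021.
- Power lost is the part of that 0.021 that would have reached significance at the end, by integration 0.0026, so 80.0% falls to about 79.7%.

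The placebo rate does not enter these formulas except through the drift. At 22%, 28% and 37% the detectable odds ratio at 80% power is 3.24, 3.08 and 2.99, so the drift barely moves over the cited rates.

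**The case against.** The best defence is that the rule performs acceptably at the rate the plan was built on. At a common 22% it stops a useless drug 33-50% of the time, comparable with the 48% of the conditional-power rule, and it hardly ever stops a drug with the planned effect. The gain from changing it lies at higher placebo rates. That stands, and it limits the point.

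Three stronger readings are tempting, and the documents do not support them:

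- **That the rule almost never stops a useless drug.** True at about 30% or more, but not at the plan's own 22%.
- **That it is likely to close the trial on an effective drug.** This needs a placebo rate near 10% or below; the plan cites none under 22% and its aims expect substantial placebo response.
- **That the 25% rationale contradicts the cited rates.** The text refers to placebo rates in the plural, and 25% lies inside the 22-37% range. The rationale is loose, not false.

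A reader might also turn to the results summary at the end of the document, where unsteadiness/dizziness responded at 18.9% versus 12%, and infer that the rule would have stopped the trial. Those are final figures for one symptom; vertigo was at 47.7% versus 57.6%. No interim data are reported, and hindsight is not a test of the plan.

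It is also fair that failing to stop a useless drug does not inflate the type I error, that section III.M treats a negative result as informative, and that one sentence on precedence would cure the overlap. None of this makes an absolute threshold a measure of comparative futility.

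**Conclusion.** The point holds in this form. The lack-of-efficacy rule ignores the between-arm difference, so its protection against continuing with a useless drug is set by the placebo rate: a third to a half of trials stopped at 22%, 5-8% at 28%, and 0.3% or less at 37%. Wrongful stopping is at most 1.6% at 38% versus 22% and 0.06% at an odds ratio of 3.2 from 22%; it reaches about 35-78% only in a hypothetical with placebo at 8-10%. The missing precedence between the two stopping rules and the uncovered value of exactly 25% are real gaps in the text, and the first is negligible in probability at the planning rates.

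These figures rest on an assumed 40:20 interim, independent attacks and a 0.05 interim test, none of which the plan states. Month 33 may yield fewer attacks than the larger columns assume. The defect should be corrected, but it does not threaten the trial at its planning rates.

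**What to change.** In section III.J, item 7:

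1. Delete the 25% stop and continue thresholds and their rationale. This also removes the gap at exactly 25%.
2. Substitute a non-binding futility rule on the between-arm effect for 1a(1), for example conditional power under an odds ratio of 3.2 below 20%, computed by an unblinded statistician for the DSMB.
3. State that the between-arm efficacy test is checked first and takes precedence, and give its interim significance level.
4. State the number of subjects or attacks that triggers the look, and report the rule's stopping probabilities over placebo rates of 22-37%, allowing for repeated attacks within subject.

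The cost is one rewritten SAP paragraph and about 0.3 points of power if the futility rule is always followed.
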